**Table PYAD.6.2. Definition of Study Period Time Intervals**

Study Period	Interval Start Definition	Interval End Definition
Screening: All patients who sign informed consent are considered as entering the Screening Period.	Informed consent date	Prior to the start of Evaluation Period.
Evaluation Period: All patients who are randomized to the study are considered as entering the Evaluation Period.	At the start of study drug administration date/time following randomization. For patients who are randomized but not dosed, the Evaluation Period starts on the date of randomization.	The minimum of Evaluation Period discontinued date, study discontinuation date, or first Follow-Up visit date.
Follow-Up: All patients who had a follow up visit are considered as entering follow-up period.	After the Evaluation Period ends.	The maximum of the last study visit date or study disposition date.

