Treatment comparisons of continuous efficacy and safety variables with a single postbaseline timepoint will be made using analysis of covariance (ANCOVA) with: (a) treatment group, (b) facility, (c) role within the facility (resident vs staff), (d) sex and (e) baseline value in the model. Type III sums of squares for LS means will be used for statistical comparison between treatment groups. The LS mean difference, standard error, p-value-, and 95% CI, unless otherwise specified, will also be reported. Missing data imputation method for the ANCOVA model is specified in Section 6.3.

Treatment comparisons for binary efficacy endpoints will be made using logistic regression. The model will include the treatment groups, facility, and the stratification factors (resident/staff and sex) as explanatory variables. For the primary and key secondary endpoints, p-values from Rao's score test (or score test) will be reported (Rao 1948). For all other endpoints, results from a Wald test will be reported. The odds ratio and the corresponding CIs, as well as the treatment differences and the corresponding CIs, will be reported.

For other binary endpoints, treatment comparisons will be made using Chi-square tests if the expected count is at least 5 in at least 80% of the cells, otherwise a Fisher's exact Test will be used.

The Kaplan-Meier (KM) product limit method will be used for time-to-event analyses. The hazard ratio and log-rank test will be reported. Time for all analyses will be described in units of days.

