#### **6.12.5. Hospitalization, Clinical Events, and Clinical Status**

The following events (observed at any time point during the study evaluation period) will be summarized using descriptive statistics:

- Proportion of participants hospitalized
- Duration of hospitalization (DOH; in days),
- proportion (percentage) of participants admitted to Intensive Care Unit (ICU),
- proportion (percentage) of participants requiring mechanical ventilation (oxygen source = “Intubation/Mechanical Ventilation”)

All hospitalization events, and procedures of special interest will be listed.

In the event that a participant has an ongoing hospitalization event at the time of study disposition, the hospitalization end date will be imputed to the study disposition date.

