#### **6.16.1.1. Time to Improvement to Mild Severity Symptoms**

Time to improvement to mild severity symptoms will be is defined (in days) as:

*(Date when participant's symptoms first meet definition of mild severity – Date when participant's symptoms first meet definition of moderate or worse severity + 1)*

Only patients who have at baseline or later develop moderate-or-worse severity COVID-19 will be included in the analysis. If a patient has not experienced improvement to mild symptoms by completion or early discontinuation of the Evaluable Period, the patient will be censored at the date of their last visit during the Evaluation Period.

Time to improvement to mild severity symptoms will be summarized by treatment group and listed for the Prevention populations and the Part 1 Treatment population. In addition, a graphical presentation of the symptom improvement will be provided using a KM plot.

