#### 6.16.1.4. Time to SARS-CoV-2 Clearance

See Section 6.16.1.3 for more details on the definition of viral clearance and date of viral clearance.

Time to SARS-CoV-2 clearance is defined (in days) as:

*(Date of first negative SARS-CoV-2 RT-PCR test – Date of first positive SARS-CoV-2 RT-PCR test + 1)*

Only patients who have at baseline or later develop SARS-CoV-2 infection will be included in the analysis. If a patient has not experienced SARS-CoV-2 clearance by completion or early discontinuation of the evaluation period, the patient will be censored at the date of their last visit during the evaluation period.

Time to SARS-CoV-2 clearance will be evaluated during the study evaluation period only and will be summarized by treatment group, and listed for the Prevention and Treatment populations. Cox proportional hazard methodology will be used.

Time to SARS-CoV-2 clearance will be presented graphically.

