#### 6.16.1.6. Duration of Hospitalization

Treatment comparisons of the mean DOH (in days) due to COVID-19 will be compared between each study intervention and placebo using a nonparametric rank-sum test (such as Mann-Whitney or van Elteren test) adjusting for facility and for the randomization stratification factors. This comparison will be made on the Prevention and Treatment populations.

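### Time to improvement and duration of hospitalization have no rule for death, so in these exploratory comparisons an arm with more deaths can look as good as or better than the other

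*SAP*

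**What the plan says.** **Time to improvement (SAP 6.16.1.1).** The endpoint counts days from first meeting moderate-or-worse severity to first meeting mild severity. It covers participants who have moderate-or-worse COVID-19 at baseline or develop it, in the Prevention populations and the Part 1 Treatment population. For those who do not improve: "If a patient has not experienced improvement to mild symptoms by completion or early discontinuation of the Evaluable Period, the patient will be censored". The date used is the last visit: "the patient will be censored at the date of their last visit during the Evaluation Period". Table PYAD.6.2 ends the Evaluation Period at "The minimum of Evaluation Period discontinued date, study discontinuation date, or first Follow-Up visit date", with no separate entry for death. The section plans a summary, a listing and a plot: "a graphical presentation of the symptom improvement will be provided using a KM plot". For time-to-event analyses in general, SAP 6.1.4 adds "The hazard ratio and log-rank test will be reported". No competing-risk method is specified.

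**Duration of hospitalization (SAP 6.16.1.6).** "Treatment comparisons of the mean DOH (in days) due to COVID-19 will be compared between each study intervention and placebo", by a rank-sum test, among those hospitalized for COVID-19. Death is not mentioned. SAP 6.12.5, in the safety section, says of a stay still open at study disposition that "the hospitalization end date will be imputed to the study disposition date".

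**Severity scale.** SAP 4.3 takes mild and moderate-or-worse from protocol Table 1. In that table Death is a row of its own, placed after Critical.

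**Other missing-data rules.** Non-responder imputation (SAP 6.3.3) is for categorical endpoints. Highest disease state imputation (SAP 6.3.6) is for the NIAID scale. Neither reaches these two endpoints.

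**The concern.** Kaplan-Meier censoring assumes that a censored participant would go on to improve at the same rate as those still followed. That is defensible for someone who moves away. It is wrong for someone who has died, because on the trial's own severity scale the outcome is known and is the worst one. Each death leaves the denominator, and the curve is drawn from the survivors.

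Duration of hospitalization has the mirror problem. Few days is the good direction, and a fatal stay ends at death. A participant who dies on hospital day 3 therefore gets a better rank than one discharged alive on day 8.

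The protocol lists both as objectives to compare between arms. They are meant to show milder illness and faster recovery, and more deaths in one arm can improve that arm's result on either.

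**Working it through.** The plan states no figure for this point, so there is nothing to reproduce. All death and recovery rates below are assumptions.

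**1. How many enter the improvement analysis.** Inputs from protocol 9.2 and SAP 5.2: about 1300 Part 1 Prevention participants randomized 1:1, a placebo rate of 4.0% for moderate-or-worse COVID-19, and a risk ratio of 0.33.
- Placebo: 650 × 0.04 = 26.
- Active: 26 × 0.33 = 8.6, about 9.

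With these numbers a few deaths can move the curve.

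**2. Looking as good: a hand example.** Take 20 moderate-or-worse cases per arm. In arm A, 8 die on day 4, 6 improve on day 8 and 6 on day 14. In arm B, 2 die on day 4, 9 improve on day 8 and 9 on day 14.
- Deaths censored, day 8: A 6/12 = 50%, B 9/18 = 50%. By day 14 both reach 100%. The curves are identical.
- Deaths kept as not improved: A 6/20 = 30%, then 12/20 = 60%. B 9/20 = 45%, then 18/20 = 90%.

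**3. Looking better: a hand example.** Again 20 per arm, with 14 in each improving one per day on days 4 to 17. The other 6 die on day 6 in A, and stay alive but unimproved to day 57 in B.
- Deaths censored: improved by day 28 is 100% in A and 70% in B. In the log-rank test, A has 14 observed against 9.75 expected, z = 1.78 in favour of the arm with six deaths.
- Deaths kept to day 57: 70% in both arms, z = 0.

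**4. Range over assumed death rates.** Assume exponential time to improvement with mean 14 days. A share q of arm A has a death time uniform on days 1 to 14, unrelated to recovery speed. Arm B has no deaths.
- Improved by day 28 without death: 1 − exp(−28/14) = 86.5%. Censoring the deaths estimates this same quantity in A.
- Chance that a marked participant dies before improving: (14/13) × [exp(−1/14) − exp(−1)] = 1.0769 × (0.9311 − 0.3679) = 0.6065.
- True share improved by day 28 in A: (1 − q) × 0.8647 + q × (1 − 0.6065).

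| q | die before improving | true share improved, A | Kaplan-Meier, A and B |
|---|---|---|---|
| 0.05 | 3% | 0.8214 + 0.0197 = 84% | 86-87% |
| 0.10 | 6% | 0.7782 + 0.0393 = 82% | 86-87% |
| 0.20 | 12% | 0.6917 + 0.0787 = 77% | 86-87% |
| 0.30 | 18% | 0.6053 + 0.1180 = 72% | 86-87% |

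A simulation with 200,000 per arm gives the same percentages.

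If the deaths fall instead on the slowest 5%, 10%, 20% or 30% of improvers, the same simulation gives Kaplan-Meier values in A of 91%, 96%, 100% and 100%, against 86-87% in B. The true shares in A are 87%, 87%, 80% and 70%. Arm A then looks better while being equal or worse.

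**5. Duration of hospitalization.** Take 10 hospitalized per arm. Arm B has stays of 8, 9, 10, 11, 12, 13, 14, 16, 20 and 25 days. Arm A has the same first six, and its last four die after 3, 4, 5 and 6 days.
- No rule for death: means are 81/10 = 8.1 and 138/10 = 13.8 days. The rank-sum U is 18 out of 100 (50 means no difference), p = 0.017 in favour of the arm with four deaths.
- Deaths given the worst value (57 days): U = 58, p = 0.57.

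**The case against.** **Death is not expressly classed as discontinuation.** Correct. Neither SAP 6.16.1.1 nor Table PYAD.6.2 says so. The treatment follows by default from one exit rule and no exception, so this is a gap to close and not a stated choice.

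**Deaths are not hidden.** A reader might infer that a mortality imbalance would be concealed. The SAP does not support that. Deaths appear by arm in hospitalization or death (6.10.3.4), deterioration (6.10.3.5), COVID-19 mortality (6.10.3.6), worst NIAID score, where 1 is death (6.16.1.2), and all-cause mortality (6.16.2.6). These tables limit the harm, but they do not correct the curve or the rank test.

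**The endpoints carry little weight.** Both are exploratory and outside the multiplicity scheme. SAP 6.16.1.1 itself plans no test, and the hazard ratio and log-rank test come only from the general rule in 6.1.4. In the Prevention populations both analyses also select on becoming ill or hospitalized after randomization, so they are not randomized comparisons, and a death rule does not cure that. This stands and sets the severity.

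**The death rates are invented.** True. Moderate illness can be met by symptoms plus a heart rate of 90 or more, and enrolment includes staff aged 18 or over, so the rate may be low. At 3% dying before improvement, the distortion in the table is about 2 to 3 percentage points.

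**Two extensions are tempting and not supported.** Time to SARS-CoV-2 clearance (6.16.1.4) has the same sentence: "If a patient has not experienced SARS-CoV-2 clearance by completion or early discontinuation of the evaluation period, the patient will be censored". But Table 1 says nothing about viral status, and the Schedule of Activities requires no swabs in hospital, so clearance at an in-hospital death may be unobserved. How to count it is an open choice of estimand. The disposition-date rule in 6.12.5 might also be read as a fault for participants who withdraw during a stay. How to impute those stays is debatable and has nothing to do with death. The rule is also not repeated in 6.16.1.6, and the point about fatal stays does not need it, because a fatal stay ends at death in any case.

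**Conclusion.** The point holds for SAP 6.16.1.1 and 6.16.1.6. Applied as written, they count a known bad outcome as uninformative in one comparison and as favourable in the other. The direction follows from the rules alone. The size rests on death rates among ill or hospitalized participants, which the documents do not give. If deaths are unrelated to recovery speed, the overstatement of improvement by day 28 under the assumed model runs from 2 to 3 points (3% dying before improving) to 14 to 15 points (18%). It is larger, and can reverse the comparison, if slow recoverers are the ones who die. A reader might take this as a threat to the trial's main conclusions. It is not one: the primary and key secondary analyses are untouched. Severity is minor, as a cheap improvement to exploratory endpoints only.

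**What to change.** - **SAP 6.16.1.1:** keep participants who die without improving in the risk set as not improved until the earlier of Day 57 and the data cut-off of the relevant database lock. Alternatively, report cumulative incidence of improvement with death as a competing event. Keep last-visit censoring for other discontinuations. The cut-off limit is needed because the Primary Database Locks (SAP 6.1.5) are event-triggered. Some survivors will still be in the Evaluation Period, and holding deaths to Day 57 past the lock would keep them at risk longer than comparable survivors.
- **SAP 6.16.1.6:** give hospitalized participants who die the worst rank in the rank-sum test, and show observed days in hospital descriptively beside it.
- **No change** on this ground to SAP 6.16.1.4 or to the handling of stays open at withdrawal.

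The cost is a few sentences in the SAP and a small programming change, with no new data. The downside is that duration of hospitalization becomes a composite of stay and death, and its table needs a footnote saying so.

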#### 6.16.1.2. Worst NIAID Score

The lowest daily value from Day 1 through the end of the Evaluation Period for a patient on the NIAID ordinal scale will be analyzed using a nonparametric rank-sum test (such as Mann-Whitney or van Elteren test) adjusting for facility and for the randomization stratification factors. Missing data will be imputed using HDSI, as described in Section 6.3.6. Mean value by treatment group will be plotted over time. This comparison will be made on the Prevention and Treatment populations.

#### 6.16.1.3. SARS-CoV-2 Clearance

For qualitative determination of viral clearance, the lab determination of “positive”/“negative” will be used. SARS-CoV-2 clearance (yes/no) is defined as a single negative RT-PCR test for the SARS-CoV-2 virus. The date of viral clearance is defined as the date of the first occurrence of a negative test.

The proportion of patients that achieve SARS-CoV-2 clearance within 1, 2, or 3 weeks of becoming SARS-CoV-2 positive will be summarized by treatment group in frequency tables and listed for the Prevention populations and the Part 1 Treatment population. Similar summaries will be made for the proportion of patients in the Part 2 Treatment and Part 3 treatment populations that achieve SARS-CoV-2 clearance within 8 and 29 days of becoming SARS-CoV-2 positive.

In addition, the number of patients that achieve SARS-CoV-2 clearance within 1, 2, or 3 weeks (or, for the Part 2 Treatment and Part 3 treatment populations, within 8 and 29 days) of becoming SARS-CoV-2 positive will be analyzed using logistic regression to compare treatment groups, if there are sufficient data available. Missing data will be imputed using the NRI method as described in Section 6.3.3. This comparison will be made on the Prevention and Treatment populations.

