### **6.1.2. Definition of Study Baseline**

Unless otherwise specified, for all measurements, baseline is defined as the last nonmissing assessment recorded on, or prior to, the date of the study drug administration at study Day 1.

Baseline SARS-CoV-2 RT-PCR and serology status will be based on evaluable test results on, or prior to, the date of study drug administration at study Day 1. A participant will be considered RT-PCR positive at baseline if any RT-PCR result is determined to be positive.

Baseline for safety analysis is described in the safety section.

Change from baseline will be calculated as the visit value of interest minus the baseline value. If a baseline value or the value at the visit is missing for a particular variable, then the change from baseline is defined as missing.

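### Viral clearance is dated at the first negative RT-PCR with no requirement that it follow the first positive, so the rule misclassifies infected Prevention participants

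*SAP*

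**What the plan says.** SAP 6.16.1.3 gives the definition: "SARS-CoV-2 clearance (yes/no) is defined as a single negative RT-PCR test for the SARS-CoV-2 virus". It dates the event as follows: "The date of viral clearance is defined as the date of the first occurrence of a negative test". The proportion cleared is summarised at 1, 2 and 3 weeks from turning positive for the Prevention populations and the Part 1 Treatment population. It is compared between arms by logistic regression if there are enough data. This section has no Evaluation Period limit.

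SAP 6.16.1.4 computes time to clearance as "Date of first negative SARS-CoV-2 RT-PCR test – Date of first positive SARS-CoV-2 RT-PCR test + 1", analysed by Cox regression. On who is included it says: "Only patients who have at baseline or later develop SARS-CoV-2 infection will be included in the analysis". On the window it says: "Time to SARS-CoV-2 clearance will be evaluated during the study evaluation period only". Participants who have not cleared are censored at their last Evaluation Period visit.

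Three other places matter.
- SAP Table PYAD.6.1 makes RT-PCR negativity at baseline part of the definition of both Prevention populations.
- SAP Table PYAD.6.2 starts the Evaluation Period, for dosed participants, thus: "At the start of study drug administration date/time following randomization". The schedule of activities in Protocol 1.3.1 takes the Day 1 swabs before dosing.
- SAP 6.1.2 sets baseline status: "A participant will be considered RT-PCR positive at baseline if any RT-PCR result is determined to be positive". Protocol 1.3.1 schedules both a nasopharyngeal and a nasal swab on Day 1.

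**The concern.** Clearance means that someone who was positive has become negative. The written rule asks only for a negative. A Prevention participant who becomes infected has, by construction, at least one negative before the first positive, so the rule picks a date before infection.

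The clearance proportions with their logistic regression, and time to clearance with its Cox model, are at stake. If every infected participant in both arms is cleared by definition, the logistic comparison carries no information. A participant who never turns negative again would be classed as cleared. Negative durations are not usable survival times. If they were dropped, the Prevention analysis would shrink largely to participants first positive at Day 8, a subset selected by infection date after randomisation. If a programmer repairs the rule silently, the rule actually used will not have been pre-specified.

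**Working it through.** The documents give no target figure, event count or power for clearance, so there is nothing to reproduce. The check applies the written rules to the visit schedule.

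**Inputs.** Prevention swabs: Day 1 (pre-dose), then Days 8, 15, 22, 29, 36, 43, 50 and 57, each post-dose visit with a window of plus or minus 2 days (Protocol 1.3.1). Let *p* be the day of the first positive and *n* the day of the first negative. Time = *n* - *p* + 1 (SAP 6.16.1.4). Assumptions: every scheduled swab is taken, all swabs before *p* are negative, and Day 57 is the last Evaluation Period swab, in line with the protocol's 8-week period.

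**Proportions, SAP 6.16.1.3.** With no Evaluation Period limit, the first negative is the baseline swab, *n* = 1. For any post-dose first positive, the clearance date precedes the start of the 1-, 2- or 3-week count and so meets each upper limit. All infected Prevention participants are therefore cleared at all three time points.

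**Time to clearance, SAP 6.16.1.4.** In dosed participants the pre-dose swab is outside the window, so the earliest usable negative is Day 8. The last column is the case of a participant who is negative at the next weekly visit.

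| First positive | As written, Evaluation Period swabs only | Negative required after the positive |
|---|---|---|
| Day 8 | valid: 15 - 8 + 1 = 8 if negative at Day 15 | 8 |
| Day 15 | 8 - 15 + 1 = -6 | 22 - 15 + 1 = 8 |
| Day 22 | 8 - 22 + 1 = -13 | 8 |
| Day 29 | -20 | 8 |
| Day 36 | -27 | 8 |
| Day 43 | -34 | 8 |
| Day 50 | -41 | 8 |
| Day 57 | 8 - 57 + 1 = -48 | censored |

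Seven of the eight possible first-positive visits give a negative time. Visit windows do not change this: the closest case is a negative on Day 10 and a positive on Day 13, 10 - 13 + 1 = -2.

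**Discordant Day 1 swabs, Part 1 Treatment.** One positive and one negative Day 1 swab make the participant baseline positive. Under 6.16.1.3 the negative swab dates clearance to Day 1. Under the 6.16.1.4 formula, time = 1 - 1 + 1 = 1 day. Both swabs precede dosing, so a strict Evaluation Period limit would exclude the negative. It would equally exclude the Day 1 positive, yet 6.16.1.4 expressly includes participants infected at baseline. The SAP does not say that the limit applies to one swab and not the other. The documents give no discordance rate. The scheduled Day 1 pair does not arise in the Part 2 Treatment Cohort or Part 3, where Protocol 1.3.2 schedules only a nasopharyngeal swab.

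**The case against.** The strongest reply is that the intended order is clear from the surrounding text. The proportions are counted from turning positive. Protocol Section 3 anchors the Part 1 endpoints to the positive RT-PCR, or to baseline in the Treatment population. The censoring rule would rarely apply to infected Prevention participants if earlier negatives counted. Negative durations in a Cox model would probably be noticed in programming. The endpoints are exploratory, they sit outside the testing scheme in SAP 6.5, and the logistic comparison is conditional on sufficient data.

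Most of this stands, and it shows that the fault lies in the wording and not in the aim. It does not make the written rule workable, because the definition and the formula in both sections omit the ordering.

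A reader might also infer two stronger things that the documents do not support.
- *All Prevention participants count as cleared.* They do not. The time analysis covers only participants with infection, the Part 1 Prevention objective covers only those who become RT-PCR positive, and the proportions need a positive date to start from.
- *The baseline swab makes every Prevention clearance time negative* (2 - *p*, for example 1 - 15 + 1 = -13 for a first positive at Day 15). In dosed participants that swab precedes the Evaluation Period, so it is not the operative negative in 6.16.1.4, and first positives at Day 8 are handled correctly. From Day 15 on, the cause is the earlier negative weekly swabs.

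**Conclusion.** The point holds for infected participants. As written, 6.16.1.3 classes all infected Prevention participants as cleared at 1, 2 and 3 weeks, and 6.16.1.4 gives -6 to -48 days for first positives at Day 15 to Day 57. The 6.16.1.4 figures assume dosed participants with complete weekly swabs. If the Day 8 swab is missed, a first positive at Day 15 has no earlier Evaluation Period negative and its time is valid.

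The Day 1 problem in the Part 1 Treatment population is possible, and its frequency cannot be judged from the documents. Never-infected participants are untouched, and so are all primary and key secondary results. The intended order can be inferred, but following the stated rule gives wrong results, so the text should be corrected.

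**What to change.** In SAP 6.16.1.3 and 6.16.1.4, define clearance as the first negative RT-PCR collected on a date after the first positive RT-PCR; for participants positive at baseline, on a date after Day 1. Use that one date for the proportions, the logistic regression and the Cox model. Requiring a later date, and not merely a later result, also settles discordant Day 1 swabs.

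Under this rule no time is negative. A participant first positive at Day 8 to Day 50 and negative at the next weekly visit has a time of 8 days, and a first positive at Day 57 is censored. The cost is one sentence in each of two SAP sections. No new data collection, sample size change or protocol amendment is needed.
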